completed electronically, when possible, but paper and telephone-based options will be available for patients not able to complete electronically. Baseline surveys should be completed within 90 days of completion of definitive therapy (chemotherapy, radiation, or surgery) for Cohort 1 (early stage) and at any time post metastatic diagnosis for Cohort 2 (metastatic). We will allow people to enroll during ongoing maintenance therapy with non-cytotoxic therapies including endocrine therapy, targeted therapy (e.g. Her2-targeted therapy) or immunotherapy. Patients will be asked to complete a follow-up survey after completion of the PRISM intervention, with a goal completion of within 60 days. We will make up to 5 attempts to reach patients if they do not complete their survey. The survey includes 114 questions at baseline and 106 questions at follow-up on feasibility, acceptability, appropriateness, recent stressors, fear of recurrence, anxiety, depression, social determinants of health, spirituality, resilience, posttraumatic growth, patient activation, and quality of life (**Table 2**). The survey is expected to take approximately 30-40 minutes to complete.

Survey responses will be captured using a database hosted by the University of North Carolina PRO Core. The staff at PRO Core will contact participants once prior to each survey due-date, and up to 4 times thereafter for missed surveys. PRO Core will oversee data monitoring and quality. PRO Core adheres to best practices for data security and privacy. PRO Core is accessed through a web interface using a secure, authenticated login. Data are stored in a secure enterprise-level Oracle database; the databases and web servers are hosted by the UNC Center for Bioinformatics. Data transmitted between the server and end-users are encrypted using SSL, and all databases are encrypted. PRO Core will store patient data in a secure database identified by a coded study ID. Upon study conclusion, the de-identified dataset will be transferred to UAB via secure transfer and stored in a password protected file for analysis.

3.5 Study Procedures- Biological Specimens (Cohort 1 Early Stage Breast Cancer Patients Only):

Blood samples:

Blood samples will be collected at baseline and approximately 6 months after surgery (post PRISM intervention, aligned with standard of care appointment where possible).

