3.6 Study Procedures- Post-intervention Interview (Both Cohorts) Upon completion of the whole intervention, participants will participate in a 30 minute to 1-hour semi-structured interview (Appendix B) to elicit perspectives on psychological state, intervention feasibility and acceptability, and areas for expansion of the intervention to better meet the needs of women with breast cancer, all the while with a focus on equity. A semi-structured interview will be conducted by a trained qualitative interviewer either in person or virtually using Zoom or by phone based on patient choice. Interviews will be audio recorded, transcribed verbatim, and stored in a secure, password-protected folder. Participants who do not complete the intervention or complete surveys will also be asked to participate in interviews to explore barriers to completion and opportunities for improvement.

| Table 2. Primary and secondary outcomes. | | | | | |
|---|--|-----------------|------------------|------------------------|--|
| Domain | Instrument or Source | Baseline | Follow-up | Number of items | Expected length of time to complete |
| Demographics | Study-specific questionnaire | X | | 9 | 2 minutes |
| Social determinants of health | CMS Health Related Social Needs | X | | 11 | 2-3 minutes |
| Spirituality | FACIT-SP | X | X | 12 | 2-3 minutes |
| Fear of cancer recurrence* | Fear of Cancer Recurrence Inventory Short Form (FCRI-SF) ¹³ | X | X | 12 | 2-3 minutes |
| Depression | Patient Health Questionnaire depression scale ¹⁴ | X | X | 8 | 2 minutes |
| Anxiety | General Anxiety Disorder-7 ¹⁵ | X | X | 7 | 2 minutes |
| Resilience | Connor Davidson Resilience Scale -10 ¹⁶ | X | X | 10 | 2-3 minutes |
| Post-traumatic growth | Post-Trumatic Growth Inventory ¹⁷ | X | X | 21 | 3-4 minutes |
| Patient activation | Patient Activation Measure (PAM) ¹⁸ | X | X | 13 | 2-3 minutes |
| Quality of life | PROMIS Global Short Form ¹⁹ | X | X | 10 | 2-3 minutes |
| Life stressor question | Study Specific Survey | X | X | 1 | 30 seconds |
| Acceptability | Acceptability of Intervention Measure (AIM) ²⁰ | | X | 4 | 1-2 minutes |
| Appropriateness | Intervention Appropriateness Measure (IAM) ²⁰ | | X | 4 | 1-2 minutes |
| Feasibility | Feasibility of Intervention Measure (FIM) ²⁰ | | X | 4 | 1-2 minutes |

*Only administered to patients with early stage breast cancer

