3.7 Compensation: Participants who complete biomarker and survey portions of the study will receive a \$50 gift card upon completion. Patients who complete the interview will receive an additional \$50 upon completion (\$100 total for Cohort 1, \$50 for Cohort 2).

3.8 Quantitative Analysis: Cohorts will be analyzed both separately and together. The primary outcome is feasibility, which will be defined as 70% of women completing all intervention components and 70% of survey time points (baseline, post-surgery, post intervention)

being completed. Secondary endpoints will include implementation outcome measures by Weiner, which will evaluate the acceptability, appropriateness, and feasibility (survey-based) of interventions.²⁰ Acceptability of Intervention Measure (AIM), Intervention Appropriateness Measure (IAM), and Feasibility of Intervention Measure (FIM) are implementation measures with four-items each, and a response scale ranging from 1 to 5 (1 = Completely disagree, 2 = Disagree, 3 = Neither agree nor disagree, 4 = Agree, 5 = Completely agree).²⁰ Scores for each measure are calculated by averaging responses.²⁰ An average of 4 or greater on each measure (AIM, IAM, FIM) will be considered acceptable, appropriate, and/or feasible.

We will also capture the following measures for future comparative efficacy trial:

- **Fear of recurrence** will be measured using the Fear of Cancer Recurrence Inventory Short Term (FCRI_SF) which is scored from 0 to 4 (0 = Not at all, 1 = A little, 2 = Somewhat, 3 = A lot, 4 = A great deal)¹³.
- **Patient depression** will be measured using the Patient Health Questionnaire depression scale¹⁴, which is a 2 questions screener with 6 additional questions for an 8 question scale with a cut-point of greater than or equal to 10 being defined as current depression.
- **Patient anxiety** will be measured using the General Anxiety Disorder-7 scale,¹⁵ which is a 7 item scale with scores of 0-4 signifying minimal anxiety, 5-9 mild anxiety, 10-14 moderate anxiety, and greater than 15 severe anxiety.
- **Resilience** using the Connor-Davidson Resilience scale which has 10 items each carry a 5 point range (0 = Not true at all, 1 = Rarely true, 2 = Sometimes true, 3 = Often true, and 4 = True nearly all of the time; total scores range from 0-40, and higher score indicate higher resilience)¹⁶

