- **Post-traumatic growth** will be measured using the Post-Traumatic Growth Inventory (PTGI), which is a 21 item questionnaire with each item scored from 0-5 with 5 being greater degree of change.¹⁷
- **Social determinants of health** will be measured using the CMS Health Related Social Needs, which is a 11 question survey.
- **Spirituality** will be measured using the FACIT-SP is 12 question instrument.
- **Patient activation** using the Patient Activation Measure scores of which range from 0 to 100 with four corresponding levels [level 1 (0.0 - 47.0), level 2 (47.1 – 55.1), level 3 (55.2 – 72.4), and level 4 (72.5 – 100) which indicates the highest level of activation]¹⁸;
- **Quality of life** using the PROMIS Global Scale which is a 10-item measure that is scored from 1 to 5 (1 = Never, 2 = Rarely, 3 = Sometimes, 4 = Often, 5 = Always).¹⁹ (Table 2)
- **Recent life stressors:** We will use a single open-ended questions asking “Have you had any additional life stressors in the last 3 months (in addition to your breast cancer diagnosis and treatment)?”

Descriptive survey statistics will be calculated using frequencies and percentages for categorical variables and medians and interquartile ranges for continuous variables. Data will be analyzed in aggregate, by race, by residence in high vs. low resource census blocks, and by presence of dependent children in the home. Pre-post changes in survey scores will be examined using mixed models repeated measures analysis with two points of data capture: surveys capturing data at baseline (T₁) and after PRISM intervention (T₂). Linear contrasts will be used to estimate average change in survey scores between timepoints and compute 95% confidence intervals. The modeling approach uses all available data. Patterns of missing data will be examined and if necessary, models will be

adjusted with covariates associated with missingness. Normality of residuals will be examined, and if found to be non-normal, generalized linear modeling will be used.

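### The plan sets no T2 survey date for women who stop PRISM early, so read literally the AIM/IAM/FIM verdicts and all T2 scores come only from women who finished

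*Combined protocol and SAP*

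**What the plan says.** All references are to the combined protocol and SAP.

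- **Section 3.4 (Surveys)** times the follow-up survey by the end of the intervention: "Patients will be asked to complete a follow-up survey after completion of the PRISM intervention", with a target of 60 days. The survey team is to "contact participants once prior to each survey due-date, and up to 4 times thereafter for missed surveys". No due date is given for a woman who stops PRISM.
- **Section 3.6 (Post-intervention Interview)** does foresee non-completion: "Participants who do not complete the intervention or complete surveys will also be asked to participate in interviews". It mentions no survey for these women.
- **Table 2** marks AIM, IAM and FIM at follow-up only, so they have no baseline value.
- **Section 3.8 (Quantitative Analysis)** sets the criterion that begins "An average of 4 or greater on each measure (AIM, IAM, FIM" and names no analysis population for it. Pre-post change is estimated by a mixed model on two occasions, baseline (T1) and after PRISM (T2). On missing data it says "The modeling approach uses all available data", with covariates related to missingness added if needed. No sensitivity analysis is described.
- **Section 3.8** also defines primary feasibility by two 70% thresholds, one for intervention components and one for survey time points. The precision statement assumes 70% completion of N=40.
- **Section 3.1** says that women who drop out are replaced until each cohort is full.

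**The concern.** The event that makes T2 due is the event the study is meant to judge. If a woman stops because PRISM was unhelpful, burdensome or badly timed, nothing in the plan schedules her to score its acceptability, appropriateness or feasibility. The mean compared with 4 is then a mean over women for whom PRISM was workable enough to finish.

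For pre-post change the mechanism differs. The mixed model keeps the baselines of women without T2, but it must predict their T2 scores from women who finished. If no non-finisher has a T2 score, completion status cannot be used as a covariate to repair this, because T2 is never observed in that group. The assumption cannot be tested.

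The changes are meant to inform a future comparative trial, and the AIM/IAM/FIM results are secondary verdicts. Scores not collected during the study cannot be recovered later.

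**Working it through.** **Inputs from section 3.8:** N=40; 70% completion; standardised outcome (SD 1); within-person correlation ρ = 0.5, 0.6, 0.7; cut-off 4 on a 1 to 5 scale. **Assumed, not in the documents:** AIM means and changes for finishers and non-finishers.

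**1. The plan's own precision figure.** With n = 0.70 × 40 = 28 pairs, half-width = t(0.975, 27) × √(2(1−ρ)) / √28. This gives 0.388, 0.347 and 0.300, against the stated 0.38, 0.35 and 0.30. The figures reproduce apart from a small gap in the first, which truncation would explain. The plan's precision therefore allows for 12 of 40 women without T2.

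**2. What the 12 extra baselines add.** With 40 baselines and 28 T2 scores under missing at random, and covariances treated as known, the variance of the estimated change is (1−ρ²)/28 + ρ²/40 + 1/40 − 2ρ/40. At ρ = 0.5 this is 0.0268 + 0.0063 + 0.0250 − 0.0250 = 0.0330, and the half-width (27 df) is 0.373. For ρ = 0.6 and 0.7 it is 0.336 and 0.294. The gain over pairs alone is small.

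**3. What the model estimates.** Let g be the all-enrolled baseline mean minus the finishers' baseline mean. The estimate is the finishers' change minus (1−ρ)g. If finishers and non-finishers start at the same mean, g = 0 and the model returns the finishers' change. With an assumed finisher change of 0.40 SD:

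- non-finishers change by 0: 0.7 × 0.40 + 0.3 × 0 = 0.28
- non-finishers change by 0.2: 0.7 × 0.40 + 0.3 × 0.2 = 0.34

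The overstatement is 0.40 − 0.28 = 0.12 or 0.40 − 0.34 = 0.06 SD.

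**4. AIM, IAM or FIM tipping value.** With completion k and finisher mean m, the all-enrolled mean falls below 4 when non-finishers average below (4 − k·m)/(1 − k).

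| k | m | Tipping value |
|---|---|---|
| 0.70 | 4.1 | 3.77 |
| 0.70 | 4.2 | (4 − 2.94)/0.30 = 3.53 |
| 0.70 | 4.3 | 3.30 |
| 0.70 | 4.5 | 2.83 |
| 0.80 | 4.2 | (4 − 3.36)/0.20 = 3.20 |
| 0.90 | 4.2 | (4 − 3.78)/0.10 = 2.20 |

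At k = 0.70 and m = 4.2, a non-finisher mean of 3.3 gives 2.94 + 0.99 = 3.93, and 3.6 gives 2.94 + 1.08 = 4.02.

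**5. Survey-completion half of the primary outcome.** Take the two time points in Table 2 (section 3.8 also lists a post-surgery one), all 40 baselines, and T2 from 28 finishers. Pooled completion is 68/80 = 85% if all T2 surveys are due, or 68/68 = 100% if only finishers' are. Both pass. The denominator matters only if each time point must reach 70%: with 25 of 28 finishers answering, T2 completion is 25/40 = 62.5% or 25/28 = 89%. Section 3.8 does not say which reading applies.

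**6. With T2 from all 40 women**, the step 1 formula (n = 40, 39 df) gives 0.320, 0.286 and 0.248.

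**The case against.** The strongest reply is that the section 3.4 sentence can be read as timing, not as a condition. It excludes no subgroup, reminders are planned for missed surveys, and sections 3.6 and 3.8 treat session completion and survey completion as separate things. A reader might infer that T2 is sent only to finishers and that women who stop will have no T2 data. The documents do not say that; they are silent on when, or whether, such a woman is surveyed. This part of the objection stands. The gap also stands, because no due date can be derived for her.

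A reader might also infer that the pre-post analysis describes completers only. That is not supported either. Non-finishers' baselines stay in the model, and covariates for missingness are allowed. The weakness there is the untestable assumption and the lack of a sensitivity analysis.

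Other mitigating points are fair. AIM/IAM/FIM are secondary. The primary outcome already counts non-completion of PRISM against feasibility. Non-finishers are invited to interviews that cover feasibility and acceptability. No formal testing is planned, and section 3.1 expects little drop-out. These limit the consequences, but an interview does not supply a score for a numerical cut-off.

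**Conclusion.** The point holds as a gap in data collection: completion of PRISM is the only stated trigger for T2, and the one stated provision for women who stop is an interview. Read literally, the AIM/IAM/FIM verdicts could be too favourable, and the pre-post estimate leans on missing at random without a check.

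The direction of bias is plausible but not proven, and its size rests on assumed scores. At 70% completion with a finisher mean of 4.2, a non-finisher mean below 3.53, still above the neutral 3, changes the verdict. At 90% completion it would have to be below 2.20. The illustrative overstatement of change, 0.06 to 0.12 SD, is smaller than the planned half-widths of 0.30 to 0.38, but unlike them it would not shrink with a larger sample.

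A reader might go further and conclude that the unclear T2 denominator decides the primary outcome. Under pooled counting it does not in the example above (85% or 100%). It could only if 70% is required at each time point. This is best classed as a cheap improvement.

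**What to change.** - **Schedule.** Send T2 to every enrolled woman still in contact. Finishers receive it after PRISM, as now. Women who stop receive it at a prespecified time from baseline that matches the finishers' expected T2 window. Avoid a rule of completion or a fixed date, whichever comes first. Six sessions have five gaps, so at two-week spacing (Table 1) they span 10 weeks, beyond the 6 to 8 weeks in section 3.3, and an early fixed date could catch slow finishers mid-intervention.
- **Trigger.** State what counts as completing PRISM. Table 1 and the text of section 3.3 number the sessions differently and include optional ones, while section 3.8 requires all components. These passages must be reconciled.
- **Denominator.** Count all enrolled women, including those later replaced, in T2 completion, and say whether the 70% applies pooled or at each time point.
- **Reporting.** Give AIM/IAM/FIM and change for all responders, with PRISM completers as a secondary display.
- **Sensitivity.** For pre-post change, vary the assumed change among women without T2, for example from zero up to that of finishers.

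The cost is protocol wording and a changed trigger at the survey centre, which already runs reminders. T2 timing will differ somewhat between finishers and others, and scores may be less favourable. Some women who stop will not respond, so the selection is reduced, not removed. If the sponsor already intends to survey women who stop, a sentence giving their T2 date settles the scheduling; the denominator and the sensitivity analysis still need stating.

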Nail sample collection and analysis: Cortisol measurements will also be derived from nail samples. Nail samples will be provided by participants using fingernail trimming clippers. They will be sent to the Bio-Analytical Redox Biology (BARB) Core at UAB for further analysis. Fingernails and toenails will be cut and stored independently until processed using the procedure previously described. Briefly, nail samples will be washed twice with 2 mL isopropanol and dried overnight. The dried nail samples will be added to a pre weighed tube containing three 5 mm steel grinding balls (Retsch) and ground using a TissueLyser II (Qiagen Venlo, Netherlands) at 30 Hz for 9 min. 1 mL of methanol will be added per 50 mg of powdered nail (w/v) and placed on a rotator for 18 h at room temperature to extract the cortisol. Samples were then centrifuged at 10,000 x g for 5 min. 800 μ L of supernatant was transferred to a clean tube and evaporated under nitrogen gas in a certified fume hood. The evaporated sample will be resuspended in 400 μ L of phosphate buffered saline per 50 mg of ground sample (w/v). Cortisol will be assayed using 25 μ L of sample according to manufacturer's protocol (Salimetrics, Salivary Cortisol Enzyme Immunoassay Kit, 1-3002, State College, PA).

3.5 Study Procedures- Intervention (Both Cohorts): Following baseline survey and biospecimen collection, participants will schedule their PRISM sessions with study staff, who will also connect them with their coach. Staff and coaches will verify best contact methods and confirm timelines with participants. Coaches will provide a calendar of sessions as appointments. Staff and/or coaches will provide session reminders via phone, email, and/or text, based on participant preference, one day and 15-minutes prior to each session.

3.6 Study Procedures- Post-intervention Interview (Both Cohorts) Upon completion of the whole intervention, participants will participate in a 30 minute to 1-hour semi-structured interview (Appendix B) to elicit perspectives on psychological state, intervention feasibility and acceptability, and areas for expansion of the intervention to better meet the needs of women with breast cancer, all the while with a focus on equity. A semi-structured interview will be conducted by a trained qualitative interviewer either in person or virtually using Zoom or by phone based on patient choice. Interviews will be audio recorded, transcribed verbatim, and stored in a secure, password-protected folder. Participants who do not complete the intervention or complete surveys will also be asked to participate in interviews to explore barriers to completion and opportunities for improvement.

| Table 2. Primary and secondary outcomes. | | | | | |
|---|--|-----------------|------------------|------------------------|--|
| Domain | Instrument or Source | Baseline | Follow-up | Number of items | Expected length of time to complete |
| Demographics | Study-specific questionnaire | X | | 9 | 2 minutes |
| Social determinants of health | CMS Health Related Social Needs | X | | 11 | 2-3 minutes |
| Spirituality | FACIT-SP | X | X | 12 | 2-3 minutes |
| Fear of cancer recurrence* | Fear of Cancer Recurrence Inventory Short Form (FCRI-SF) ¹³ | X | X | 12 | 2-3 minutes |
| Depression | Patient Health Questionnaire depression scale ¹⁴ | X | X | 8 | 2 minutes |
| Anxiety | General Anxiety Disorder-7 ¹⁵ | X | X | 7 | 2 minutes |
| Resilience | Connor Davidson Resilience Scale -10 ¹⁶ | X | X | 10 | 2-3 minutes |
| Post-traumatic growth | Post-Trumatic Growth Inventory ¹⁷ | X | X | 21 | 3-4 minutes |
| Patient activation | Patient Activation Measure (PAM) ¹⁸ | X | X | 13 | 2-3 minutes |
| Quality of life | PROMIS Global Short Form ¹⁹ | X | X | 10 | 2-3 minutes |
| Life stressor question | Study Specific Survey | X | X | 1 | 30 seconds |
| Acceptability | Acceptability of Intervention Measure (AIM) ²⁰ | | X | 4 | 1-2 minutes |
| Appropriateness | Intervention Appropriateness Measure (IAM) ²⁰ | | X | 4 | 1-2 minutes |
| Feasibility | Feasibility of Intervention Measure (FIM) ²⁰ | | X | 4 | 1-2 minutes |

*Only administered to patients with early stage breast cancer

3.7 Compensation: Participants who complete biomarker and survey portions of the study will receive a \$50 gift card upon completion. Patients who complete the interview will receive an additional \$50 upon completion (\$100 total for Cohort 1, \$50 for Cohort 2).

3.8 Quantitative Analysis: Cohorts will be analyzed both separately and together. The primary outcome is feasibility, which will be defined as 70% of women completing all intervention components and 70% of survey time points (baseline, post-surgery, post intervention)

being completed. Secondary endpoints will include implementation outcome measures by Weiner, which will evaluate the acceptability, appropriateness, and feasibility (survey-based) of interventions.²⁰ Acceptability of Intervention Measure (AIM), Intervention Appropriateness Measure (IAM), and Feasibility of Intervention Measure (FIM) are implementation measures with four-items each, and a response scale ranging from 1 to 5 (1 = Completely disagree, 2 = Disagree, 3 = Neither agree nor disagree, 4 = Agree, 5 = Completely agree).²⁰ Scores for each measure are calculated by averaging responses.²⁰ An average of 4 or greater on each measure (AIM, IAM, FIM) will be considered acceptable, appropriate, and/or feasible.

We will also capture the following measures for future comparative efficacy trial:

- **Fear of recurrence** will be measured using the Fear of Cancer Recurrence Inventory Short Term (FCRI_SF) which is scored from 0 to 4 (0 = Not at all, 1 = A little, 2 = Somewhat, 3 = A lot, 4 = A great deal)¹³.
- **Patient depression** will be measured using the Patient Health Questionnaire depression scale¹⁴, which is a 2 questions screener with 6 additional questions for an 8 question scale with a cut-point of greater than or equal to 10 being defined as current depression.
- **Patient anxiety** will be measured using the General Anxiety Disorder-7 scale,¹⁵ which is a 7 item scale with scores of 0-4 signifying minimal anxiety, 5-9 mild anxiety, 10-14 moderate anxiety, and greater than 15 severe anxiety.
- **Resilience** using the Connor-Davidson Resilience scale which has 10 items each carry a 5 point range (0 = Not true at all, 1 = Rarely true, 2 = Sometimes true, 3 = Often true, and 4 = True nearly all of the time; total scores range from 0-40, and higher score indicate higher resilience)¹⁶
- **Post-traumatic growth** will be measured using the Post-Traumatic Growth Inventory (PTGI), which is a 21 item questionnaire with each item scored from 0-5 with 5 being greater degree of change.¹⁷
- **Social determinants of health** will be measured using the CMS Health Related Social Needs, which is a 11 question survey.
- **Spirituality** will be measured using the FACIT-SP is 12 question instrument.
- **Patient activation** using the Patient Activation Measure scores of which range from 0 to 100 with four corresponding levels [level 1 (0.0 - 47.0), level 2 (47.1 – 55.1), level 3 (55.2 – 72.4), and level 4 (72.5 – 100) which indicates the highest level of activation]¹⁸;
- **Quality of life** using the PROMIS Global Scale which is a 10-item measure that is scored from 1 to 5 (1 = Never, 2 = Rarely, 3 = Sometimes, 4 = Often, 5 = Always).¹⁹ (Table 2)
- **Recent life stressors:** We will use a single open-ended questions asking “Have you had any additional life stressors in the last 3 months (in addition to your breast cancer diagnosis and treatment)?”

Descriptive survey statistics will be calculated using frequencies and percentages for categorical variables and medians and interquartile ranges for continuous variables. Data will be analyzed in aggregate, by race, by residence in high vs. low resource census blocks, and by presence of dependent children in the home. Pre-post changes in survey scores will be examined using mixed models repeated measures analysis with two points of data capture: surveys capturing data at baseline (T₁) and after PRISM intervention (T₂). Linear contrasts will be used to estimate average change in survey scores between timepoints and compute 95% confidence intervals. The modeling approach uses all available data. Patterns of missing data will be examined and if necessary, models will be

adjusted with covariates associated with missingness. Normality of residuals will be examined, and if found to be non-normal, generalized linear modeling will be used.

No formal power calculation is needed for this pilot study as feasibility is defined by patient participation and completion of surveys. Following NIH guidelines, no formal testing will be conducted. Uncertainty of pre-post change estimates will be measured with 95% confidence intervals. Assuming 70% completion in the full sample (N=40), a standardized outcome, and intra-subject correlation values 0.5, 0.6, and 0.7, the upperbound half-widths of 95% confidence intervals for pre-post change are 0.38, 0.35, and 0.30, respectively. These provide reasonable ranges for potential values of change that can be expected in a future project (computations in PASS 23 software).

3.9 *Biomarker evaluation:* Data from biomarkers and ePROs will be merged with demographic data using a study ID and date of collection. We will assess the relationship between biomarker outcomes and patient-reported outcomes. We will assess for correlational trends that would support evaluation in a larger cohort. We will examine distribution and ranges of biomarker data and determine whether variance stabilizing transformations are needed such as a natural logarithm, prior to analysis. As described above, we will employ a similar quantitative approach to compare pre/post intervention differences in assessed levels of cortisol, allostatic load, DAMPs and inflammatory response biomarkers (cytokines).

3.10 *Data linkage:* Both ePRO data and the data from biospecimens will be labeled using a Study ID. A separate tracking log will be kept with Study ID and MRN at UAB. This tracking log will be used to link datasets for analytic purposes.

3.11 *Qualitative Analysis:* The analytic strategy is informed by content analysis, which classifies text into categories that represent key concepts.²¹ In the initial stages of coding, two independent coders will read the transcripts and develop an open coding scheme.²² This initial coding scheme will consider the complexities of the lived experience of women with breast cancer, with particular emphasis on the wide range of factors that contribute to their experience of recurrence and generalized stress in their daily lives. The intention here is to construct a grounded, emic measure of vulnerability that can be directly compared to outcome variables within the study and accurately identifies areas within the PRISM intervention that require adjustment for this population. Analytic codes constructed in the context of open coding are provisional and will be grounded within the data.²³ The final version of the coding schema will be reviewed and finalized by the multidisciplinary team, which will include the interviewer, two primary coders, and the study PI, all having experience in oncology, anthropology, and/or implementation science. The two primary coders will subsequently use Dedoose to conduct “focused coding,” which includes a detailed analysis of themes identified during open coding. Discrepancies will be resolved by a third coder. The process will be repeated until thematic saturation is reached, where no new categories or relevant themes emerge.²⁴ Data will be analyzed in aggregate, by race, by residence in low resource areas, and by presence of dependent children in the home. During coding, we will consult regularly with the research team for multiple perspectives and discrepancy resolution through consensus. The coders will also code 20% of the transcripts to evaluate interrater reliability using a kappa statistic. If the kappa statistic is <0.7, the coders will discuss discrepancies, refine the code book, and complete another 20% of transcripts until the

kappa reaches 0.7.²⁵ Summaries will be reviewed with the research team and key partners for the future R01 to plan for next steps in the research.

3.12 *Sample size considerations:* Using a sample of 30 patients for breast cancer (10 MBC, 30 EBC) will provide initial data on feasibility, while larger studies will be needed for formally testing outcomes. Sampling for qualitative inquiries is sequential and targeted to individuals who can provide insights on the processes under study. Typically, qualitative approaches require <30 participants to reach thematic saturation. If thematic saturation is not reached, we will engage additional participants in the intervention and continue interviews until thematic saturation is reached.

3.13 *Mixed methods analysis:* We will validate our findings using both quantitative and qualitative methodologies that will be analyzed independently through side-by-side comparisons and thoroughly integrated using grounded measures derived from the interviews themselves. This mixed methodology will ensure that study findings are grounded in the appropriate context and will provide a comprehensive view of both study feasibility and necessary adaptations prior to conducting a future comparative efficacy trial.

4 **Dissemination:** We will utilize the descriptive data from the biomarker and patient-reported outcomes evaluation in combination with existing literature to generate a lecture for patients and physicians on stress in breast cancer.

5. **Data and Safety Monitoring**

Access to patient data will be limited to the medical care teams and relevant study staff. Data will be de-identified when possible and encrypted to enhance security. Data files sent between members of the research team will be de-identified. When unique patient identifiers (unrelated to any patient characteristics) are required to track patient-level outcomes, the files will be sent via secure transfer and stored on secure encrypted network drives. All qualitative data from participant interviews will be de-identified and securely stored on password-protected, encrypted network drives.

Multiple measures will be taken to ensure that the use of structured electronic medical record (EMR) data and manually abstracted EMR data involves the highest security precautions so that risks to individuals are limited. The data storage facility is located in a building with 24-hour security. The computers and data files are only accessible via a private gigabit-speed local area network to which only research team and clinical staff are connected. No routine traffic (e-mail, web, or other non-study services) travels on this network. All data are transmitted to investigators' workstations in an encrypted state. Only members of the research team and clinical staff will have access to identifiable data. All research team members will be trained in data security. All quantitative analyses reported from this study will contain only aggregate data. The qualitative data (e.g. quotes) from individual participants will be anonymously reported. The quality of the data will be monitored on a regular basis by members of the research team under the supervision of the Principal Investigator ([name]) and statistician.

6. **Benefits**

Study participants may benefit from the intervention by improving resilience and psychological distress not only as it relates to their fear of cancer recurrence but skills learned in this intervention can be applied to multiple areas of their lives. Our findings could

benefit future patients with cancer by equipping patients with the knowledge and skills to improve stress management, resilience, and engagement with health care team.

7. Risks

Participants will not receive any pharmacologic treatment as part of this study, minimizing physical risks. This project will make use of health and other personal information about the study participants. The primary risk to the participants will be loss of confidentiality leading to potential psychological, financial, or legal consequences. However, using the data access and protection plan described above, we believe that the likelihood of confidentiality breach is very low. An additional risk that some PRISM sessions explore stressors, in turn prompting additional awareness of stress and corresponding distress. All coaches are trained in distress-recognition and suicide prevention; in >500 PRISM deliveries, there has been a single participant who endorsed significant distress prompting immediate coach intervention and referral (see Appendix Manual for procedures). In any case where coaches are concerned about participant distress, they will immediately contact the PI and the on-call social worker. In our experience, stress and distress during the sessions is short-lived and self-limited. Finally, there may be risk of discomfort from blood draws, although these will be completed in conjunction where possible with routine lab evaluations to prevent the need for additional venupuncture.

8. Confidentiality

Patients included in this study will be adult women receiving cancer care at UAB. The major risk for the study will be the risk of breach of data confidentiality. This will be minimized as described above in the data and safety monitoring section.

9. Clinical Trial Registration:

- Following initial IRB approval, this trial will be registered on ClinicalTrials.gov. All protocol revisions and estimated timelines will be reported within the system immediately following Institutional Review Board (IRB) approval.
- Results information will be submitted to ClinicalTrials.gov as outlined in the website's policy and according to the specific timelines stated therein.
- Informed consent documents for the clinical trial(s) will include a specific statement relating to posting of clinical trial information at ClinicalTrials.gov.

REFERENCES:

